16.2. SECONDARY EFFICACY

The secondary efficacy analyses will be performed for the mITT population. These include:

- Change from baseline FEV₁ to peak FEV₁ on Day 1 and at Weeks 6, 12 and 24
- Change from baseline (i.e. mean over the last 7 days of run-in) to the mean weekly value at Weeks 6, 12 and 24 in COPD symptoms, as measured by daily diary (E-RSTM:COPD)
- Change from baseline in the SGRQ total score at Weeks 6, 12 and 24
- Change from baseline FEV₁ to morning trough FEV₁ at Weeks 6, 12 and 24
- Change from baseline FEV₁ to average FEV₁ AUC_{0-4h} on Day 1 and at Weeks 6, 12 and 24
- Proportion of SGRQ responders at Weeks 6, 12 and 24
- Change from baseline (i.e. mean over the last 7 days of run-in) to the mean weekly value in the number of puffs of rescue medication at Weeks 6, 12 and 24
- TDI questionnaire at Weeks 6, 12 and 24
- Change from baseline FEV₁ to evening trough FEV₁ at Week 12

16.2.1. SECONDARY EFFICACY VARIABLES & DERIVATIONS

16.2.1.1. Spirometry

Spirometry measurement's best test time which is used in the analysis is measured in ERT and first time for spirometry measurements is measured in the eCRF and will be listed alongside the ERT best time.

Peak FEV₁ will be computed as the maximum value in the 4 hours after dosing (4 timepoints after dosing: 30 minutes, 1 hour, 2 hours and 4 hours). Baseline FEV₁ is the average of the two measurements taken before study medication on the day of first dosing, i.e. ≤40 minutes pre-dose on Day 1.

Average FEV₁ AUC_{0-4h} is calculated as described in section 16.1.1.1 of the SAP.

Morning trough FEV₁ is the last value collected prior to the morning dose.

Evening trough FEV₁ is the value collected at the 12 hours post-morning dose timepoint and prior to the evening dose.

All measurements, including unscheduled measurements, within specified time period will be used for deriving parameters; for scheduled 12 hours post-morning dose measurement use regardless of being within specified time period.

16.2.1.2. Questionnaires

16.2.1.2.1. E-RS™:COPD

EXACT-Respiratory Symptoms for COPD (E-RS™: COPD) data will be collected within EXACT-PRO questionnaire (consisting of 14 questions), as shown in Appendix 3. Please note that items 3, 8, 9, 10, 11 and 14 have separate scoring instructions, namely with the same raw score being assigned to several answer options. E-RS™: COPD consists of 11 questions, with subdomains of: Breathlessness, Cough and Sputum, and Chest Symptoms. This data will be collected everyday throughout the duration of the study.

Calculating the score

E-RS subdomains:

- Breathlessness – items 7, 8, 9, 10 and 11 (score range: 0-17)
- Cough and Sputum – items 2, 3 and 4 (score range: 0-11)
- Chest Symptoms – items 1, 5 and 6 (score range: 0-12)

The E-RS Total score is derived as the sum of the raw scores of the 11 items (score range: 0-40). Total and subdomain scores are derived weekly as the mean over the days within each window, as specified in the section 6.4 of the SAP, using only days where data was recorded. Baseline is the mean over the 7 days prior to the first intake of study treatment, using only days where data was recorded. If less than 4 days of data are available for the week, the weekly mean is set to missing. Furthermore, all questions need to be answered to be evaluable for that day.

If a patient discontinued then use treatment study end date, as the date of their last expected visit.

The EXACT-PRO total score will be calculated by first summing the raw scores of all 14 items (score range: 0-51) and then looking up the corresponding EXACT-PRO total score in the table described in the APPENDIX 4 (converted score range: 0-100).

E-RS subdomain score is calculated as the sum from the relevant questions.

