6. GENERAL CONSIDERATIONS

6.1. REFERENCE DATES AND STUDY DAY

Study Day will be calculated from the reference start date and will be used to show start/stop day of assessments and events.

Reference start date is defined as the day of the first dose of study medication (Day 1 is the day of the first dose of study medication) and will appear in every listing where an assessment date or event date appears.

- If the date of the event is on or after the reference start date, then:
Study Day = (date of event – reference start date) + 1.
- If the date of the event is prior to the reference start date, then:
Study Day = (date of event – reference start date).

In the situation where the event date is partial or missing, the date will appear partial or missing in the listings, and Study Day, and any corresponding durations will be presented based on the imputations specified in Appendix 2 of the SAP.

Reference end date is defined as the date of the last dose of study medication.

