16.2.2.3. MI method – range data

The sensitivity analysis for key secondary endpoints (SGRQ total score and weekly mean E-RS total score), the main analysis of TDI and EQ-5D-5L will be performed using MI based on the missing data assumption MAR as described in the section 16.2.2.1 of the SAP. Additionally, in the first 2 steps the MIN= and MAX= options will be used to restrict the possible values that can be drawn referred to each endpoint (Laura Rodwell, 2014).

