16.2.3. ANALYSIS OF SECONDARY EFFICACY VARIABLES

16.2.3.1. Change from baseline variables, incl. TDI

All variables used in change from baseline analysis (incl. average FEV₁ AUC_{0-4h}, peak FEV₁, morning trough FEV₁, evening trough FEV₁, mean weekly E-RS™: COPD, SGRQ, mean weekly rescue medication and TDI) will be analyzed using ANCOVA approach, as described in section 16.1.3 of the SAP. BDI will be used as a baseline for TDI. Missing data will be imputed using imputation described in section 16.2.2.3 of the SAP.

Model assumptions will be tested and solved, if failed, as per section 16.1.3 of the SAP.

A plot of the mean change from baseline FEV₁ to each post-dose FEV₁ result over time will be created by subgroups of actual background medication strata and actual smoking strata, visit and treatment group.

A plot of the least squares means change from baseline to event over time will be presented (based on the ANCOVA analysis). Events will include weekly mean total E-RS score, SGRQ and weekly mean rescue medication use.

Only FEV₁ measurements with BTR grades “Acceptable” and “Borderline Acceptable” are used in the analysis.

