16.3.1.7. E-RS total score responder

E-RS total score responder is defined as a decrease from baseline in the week mean total of E-RS score greater than or equal to 2.

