APPENDIX 3. ANNOTATED EXACT FOR RAW SCORE ASSIGNMENT

1. Did your chest feel congested today?	0. Not at all
	1. Slightly
	2. Moderately
	3. Severely
	4. Extremely
2. How often did you cough today?	0. Not at all
	1. Rarely
	2. Occasionally
	3. Frequently
	4. Almost constantly
3. How much mucus (phlegm) did you bring up when coughing today?	0. None at all
	1. A little
	1. Some
	2. A great deal
	3. A very great deal
4. How difficult was it to bring up mucus (phlegm) today?	0. Not at all
	1. Slightly
	2. Moderately
	3. Quite a bit
	4. Extremely
5. Did you have chest discomfort today?	0. Not at all
	1. Slight
	2. Moderate
	3. Severe
	4. Extreme
6. Did your chest feel tight today?	0. Not at all
	1. Slightly
	2. Moderately
	3. Severely
	4. Extremely
7. Were you breathless today?	0. Not at all
	1. Slightly
	2. Moderately
	3. Severely
	4. Extremely

8. Describe how breathless you were today	0. Unaware of breathlessness
	1. Breathless during strenuous activity
	2. Breathless during light activity
	3. Breathless when washing or dressing
	3. Present when resting
9. Were you short of breath today when performing your usual personal care activities like washing or dressing?	0. Not at all
	1. Slightly
	2. Moderately
	3. Severely
	3. Extremely
10. Were you short of breath today when performing your usual indoor activities like cleaning or household work?	0. Not at all
	1. Slightly
	2. Moderately
	3. Severely
	3. Extremely
11. Were you short of breath today when performing your usual activities outside the home such as yard work or errands?	0. Not at all
	1. Slightly
	2. Moderately
	3. Severely
	3. Extremely
12. Were you tired or weak today?	0. Not at all
	1. Slightly
	2. Moderately
	3. Severely
	4. Extremely
13. Last night, was your sleep disturbed?	0. Not at all
	1. Slightly
	2. Moderately
	3. Severely
	4. Extremely
14. How scared or worried were you about your lung problems today?	0. Not at all
	1. Slightly
	2. Moderately
	3. Severely

	3.Extremely
--	-------------

**APPENDIX 4. RAW SUMMED SCORE TO SCALE CONVERSION
 TABLE FOR EXACT TOTAL SCORE**

Raw Summed Score	EXACT Total Score	Raw Summed Score	EXACT Total Score
0	0	26	50
1	8	27	51
2	13	28	52
3	17	29	53
4	20	30	54
5	23	31	55
6	25	32	57
7	27	33	58
8	28	34	59
9	30	35	60
10	31	36	61
11	33	37	63
12	34	38	64
13	36	39	65
14	37	40	67
15	38	41	68
16	39	42	70
17	40	43	72
18	41	44	73
19	42	45	75
20	43	46	77
21	44	47	80
22	46	48	83
23	47	49	87
24	48	50	92
25	49	51	100

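### The SAP's E-RS item key tops out one point below the stated Breathlessness and Total ranges, and diary weeks for patients who stay in the study can include run-in days

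*SAP*

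**What the plan says.** **Scoring.** SAP 16.2.1.2.1 gives Breathlessness as "items 7, 8, 9, 10 and 11 (score range: 0-17", Cough and Sputum as 0 to 11, and Chest Symptoms as 0 to 12. E-RS Total is the "sum of the raw scores of the 11 items (score range: 0-40". The 14-item EXACT-PRO raw sum is given as 0 to 51. The same section says that "items 3, 8, 9, 10, 11 and 14 have separate scoring instructions, namely with the same raw score being assigned to several answer options". Appendix 3 is the SAP's only item-level key. Item 9, for example ("Were you short of breath today when performing your usual personal care activities like washing or dressing"), has five options scored 0, 1, 2, 3 and 3.

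**Use of the score.** E-RS Total at Week 24 is third in the SAP 7.4 hierarchy. A responder (16.3.1.7) has a "decrease from baseline in the week mean total of E-RS score greater than or equal to 2". For bounded imputation, 16.2.2.3 says that "in the first 2 steps the MIN= and MAX= options will be used to restrict the possible values that can be drawn", without giving numbers.

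**Diary weeks.** SAP 6.4 has two lists. For patients who leave before Week 24, Week 1 starts no earlier than Day 1. For patients who complete, or who stop study drug but stay in the study, Week 1 runs from the actual Week 24 visit day minus 168 to minus 161, with no lower limit at Day 1. SAP 6.1 sets the numbering: "Day 1 is the day of the first dose of study medication", and there is no Day 0.

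**The concern.** A programmer who follows Appendix 3 produces scores that cannot reach the maxima in 16.2.1.2.1. If the key is wrong, an alpha-controlled endpoint is mis-scored whenever a patient chooses the top option of the affected item. If the ranges are wrong, an upper imputation limit taken from them is one point too high. How far that limit reaches is itself unclear. SAP 16.2.2.3 calls bounded imputation a sensitivity analysis for E-RS. But 16.2.3.1, which covers the change-from-baseline ANCOVA including E-RS, says: "Missing data will be imputed using imputation described in section 16.2.2.3 of the SAP".

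The missing floor lets run-in days, some of them also baseline days, count as post-baseline data in the early weekly means of E-RS and rescue use. The rule in 16.2.1.2.1 and 16.2.1.3 that requires 4 recorded days does not prevent this, because run-in diary days are recorded days.

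**Working it through.** **1. Maximum scores from Appendix 3**

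Items 3, 8, 9, 10, 11 and 14 have a maximum of 3. The other eight have a maximum of 4.

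| Score | Sum of item maxima | Key gives | SAP states |
|---|---|---|---|
| Cough and Sputum (2, 3, 4) | 4+3+4 | 11 | 11 |
| Chest Symptoms (1, 5, 6) | 4+4+4 | 12 | 12 |
| Breathlessness (7 to 11) | 4+3+3+3+3 | 16 | 17 |
| E-RS Total | 11+12+16 | 39 | 40 |
| EXACT-PRO raw (adds 12, 13, 14) | 39+4+4+3 | 50 | 51 |

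Two subdomains agree, so the conflict lies in items 7 to 11. Raising any one of items 8 to 11 to a maximum of 4 gives 17, 40 and 51 together. Appendix 4 has a row for raw 51 (converted to 100), while the key stops at 50 (converted to 92).

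A lost table row is not evident. All 14 items show five options, and the shared-score items in Appendix 3 are exactly the six named in 16.2.1.2.1. A five-option item rising from 0 in unit steps with one tie cannot exceed 3.

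**2. Diary weeks**

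Let v be the study day of the Week 24 visit. The nominal day is 169 (end of Week 24 in the list for patients who leave). The visit window of ±10 days gives v = 159 to 179. Week 1 is v−168 to v−161, both included. At v = 169 this gives Days 1 to 8, matching the other list.

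| v | Week 1 | Run-in days | Post-dose days | Post-dose share |
|---|---|---|---|---|
| 159 | −9 to −2 | 8 | 0 | 0% |
| 160 | −8 to −1 | 8 | 0 | 0% |
| 161 | −7 to −1 | 7 | 0 | 0% |
| 162 | −6 to 1 | 6 | 1 | 14% |
| 163 | −5 to 2 | 5 | 2 | 29% |
| 164 | −4 to 3 | 4 | 3 | 43% |
| 165 | −3 to 4 | 3 | 4 | 57% |
| 166 | −2 to 5 | 2 | 5 | 71% |
| 167 | −1 to 6 | 1 | 6 | 86% |
| 168 | 1 to 7 | 0 | 7 | 100% |

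At v = 161, Week 1 is the same seven days as the E-RS baseline, so the Week 1 change is zero by construction. At v = 159, Week 2 also takes Day −1. Even at v = 159, Week 6 is Days 27 to 33, Week 12 is Days 69 to 75 and Week 24 is Days 153 to 159, all post-dose.

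If weeks are counted by calendar date instead, run-in days appear for v = 159 to 168. The wholly pre-dose range stays 159 to 161.

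**3. How many patients**

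The documents give no distribution of visit days. As an assumption, take v as Normal with mean 169, rounded to whole days and truncated to 159 to 179:

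| SD (days) | Any run-in day in Week 1 (v ≤ 167) | Under 4 post-dose days (v ≤ 164) | Wholly pre-dose (v ≤ 161) |
|---|---|---|---|
| 2 | 22.7% | 1.2% | 0.01% |
| 4 | 35.3% | 12.7% | 2.6% |
| 6 | 39.3% | 20.3% | 7.1% |

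**The case against.** Both discrepancies are real; the case on the other side is about reach.

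- **Imputation limit.** SAP 16.2.2.3 gives no number, so a limit of 40 is a supposition. SAP 16.2.2.1 puts weekly E-RS under unbounded imputation, and 16.2.2.3 and 16.2.4 both treat the bounded version as a sensitivity analysis. Only the pointer in 16.2.3.1 says otherwise, and it may be a cross-reference slip. This stands as a limit: the main analysis is reached only on the literal reading of 16.2.3.1.
- **Scoring effect.** One key serves both arms and baseline, so a change score moves only if use of the top option shifts between baseline and the later week. This stands. Setting a 1-point ceiling on an absolute score beside a 2-point change threshold gives scale, not an expected bias.
- **Windows.** The efficacy time points are Weeks 6, 12 and 24. Week 1 enters only the first imputation step, and the second step uses only weeks matching scheduled visits. This stands, so the effect is indirect. The exact match with baseline at v = 161 depends on study-day numbering; by calendar date Week 1 would be Days −8 to −1.
- **Cost.** A floor makes some Week 1 means missing in that same imputation step. This is true and is counted in the cost of the fix.
- **Two defects.** They are independent and can be corrected separately.

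None of this removes the contradiction in the scoring of a hierarchical endpoint, or explains why only one group of patients has a Day 1 floor.

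**Conclusion.** Both points hold.

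The key and the stated ranges differ by one point, within the Breathlessness items, and which is wrong cannot be settled from the documents. If the key is wrong, a weekly mean is off by at most 1 point, and by that much only when every recorded day is at the top option of one item. That is half the responder threshold of 2. If the ranges are wrong, only imputed values between 39 and 40 are affected, and none is shown to occur.

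The diary-week rule admits run-in days for in-window visits on Days 159 to 167. The share of patients affected rests entirely on the assumed spread of visit days: about 23% to 39% with some run-in day in Week 1, and about 0.01% to 7.1% with Week 1 wholly pre-dose.

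Neither point is shown to alter the Week 24 E-RS result. Both should be corrected before unblinding, because a scoring rule settled afterwards could look data-driven.

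**What to change.** 1. Before database lock, check Appendix 3 items 7 to 11 and the ranges in 16.2.1.2.1 against the instrument's scoring manual, and correct whichever is wrong. Align the EXACT-PRO raw range and Appendix 4 with the result. State the matching numeric lower and upper limits for E-RS in 16.2.2.3.
2. Add to SAP 6.4 that no day before first dose may enter any post-baseline diary week, as is already so for patients who leave the study. This also removes Day −1 from Week 2 at a Day 159 visit. The existing 4-day rule then decides whether Week 1 is evaluable.

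The work is SAP text and derivation code. The analytic cost is that Week 1 becomes missing for visits on Days 159 to 164 and rests on 4 to 6 days for Days 165 to 167. Under the assumed SDs of 2, 4 and 6 days, about 1%, 13% and 20% of staying patients lose Week 1. Weeks 6, 12 and 24 do not change. The floor does not address late visits, where early days belong to no week (Days 1 to 10 at a Day 179 visit); that is a separate choice.

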16.2.1.2.2. SGRQ

St. George's Respiratory Questionnaire (SGRQ) is a questionnaire consisting of 17 questions, split into two parts. Part 1 consists of the first 8 questions and is related to the Symptoms subdomain. The remaining 9 questions are in Part 2, which are related to the Activity and Impacts subdomains. Each possible answer to each question has a weight assigned described in the APPENDIX 5.

Note that question 6 (How long did the worst respiratory attack last?) has an additional instruction, “Go to Question 7 if you did not have a severe attack”. If question 6 has not been answered, it will be assigned a weight of zero.

Calculating the score

Subdomains:

- Symptoms – items 1 to 8
- Activity – items 11 and 15
- Impacts – items 9, 10, 12, 13, 14, 16 and 17

The score for each component is calculated separately by dividing the summed weights by the maximum possible weight for that component and expressing the result as a percentage. It is not possible to have missing items in the questionnaire, as the data are collected in an electronic tablet which doesn’t allow patients to skip between items.

$$\text{Component score} = 100 * \frac{\text{Sum of weights from all positive items in that component}}{\text{Sum of maximum weights for all items in that component}}$$

The total score is calculated similarly

$$\text{Total score} = 100 * \frac{\text{Sum of weights from all positive items in that questionnaire}}{\text{Sum of maximum weights for all items in that questionnaire}}$$

The higher the score the more severe impact of COPD on patient’s life.

Sum of maximum possible weights for each component and Total:

Symptoms = 662.5

Activity = 1209.1

Impacts = 2117.8

Total = 3989.4

16.2.1.2.3. BDI/ TDI

Baseline Dyspnea Index (BDI) and Translational Dyspnea (TDI) are questionnaires that focus on three subdomains: Functional impairment, Magnitude of task and Magnitude of effort. BDI is collected at baseline (Day 1) and TDI is collected post-baseline (Weeks 6, 12 and 24).

Subdomain score is calculated as the sum from the related questions.

Total score is calculated as the sum of the subdomain scores.

If at least one of the scores is missing, then total score is set to missing.

16.2.1.3. Rescue Medications

Baseline use of rescue medication is the mean over the last 7 days of run-in phase, using only days where data was recorded:

$$\frac{\text{Sum of number of puffs taken}}{\text{days recorded}}$$

Use of medication per week is calculated as the mean use daily over 7 days, as described in the windowing conventions section of the SAP, calculated only based on the days data was recorded/verified.

If less than 4 days of data are available for the week, the weekly mean is set to missing.

If a patient discontinued then use study discontinuation end date, as the date of their last expected data input.

This will be documented as Albuterol/Salbutamol in the “Rescue Medication” page of the eCRF, as well as in the “Rescue Medication Use” diary entry.

The rescue medication use will be confirmed in the diary using the following rules:

1. If patient has put in rescue medication use then analyze as expected
2. If patient has not put in rescue medication use, then to confirm that there was no diary compliance issue, or IT issue, question “No Rescue Medication Confirmation” will be checked to make sure it is filled in correctly.
3. If patient has not put in rescue medication use and question “No Rescue Medication Confirmation” was not filled in correctly then this will be treated as diary compliance or IT issue and therefore this day will not be used as the day recorded for the weekly means calculation.

16.2.2. MISSING DATA METHODS FOR SECONDARY EFFICACY VARIABLES

16.2.2.1. MI method – continuous data

The analysis for key secondary endpoints (FEV₁ AUC_{0-4h}, peak FEV₁, morning trough FEV₁, SGRQ total score and weekly mean E-RS total score) and for evening trough FEV₁ and weekly rescue medication will be performed using MI based on the missing data assumption MAR.

This process will follow four steps (below the example uses baseline FEV₁, but it is repeated also for baseline of other key secondary endpoints mentioned above, excluding the ones evaluated weekly):

1. Partially impute the data for a monotone missing pattern with 100 as a number of

imputations and “20905” as seed number. Employ the Markov Chain Monte Carlo (MCMC) method with treatment, region, background medication strata, smoking strata, baseline FEV₁ and <Visit data>. <Visit data> corresponds to all scheduled visits available for the parameter analyzed. Each visit will correspond to a covariate within the model.

The following SAS codes will be used:

```
proc mi data=<data1> out=<data2> nimpute=100 seed=20905;
  var <treatment> <region> <BackgroundMedStrata> <SmokingStrata>
  <baseline> <visits>;
  mcmc impute=monotone chain=multiple;
run;
```

2. Impute the monotone data using a regression imputation model. Apply by imputation using seed number “20905” with treatment, region, background medication strata, smoking strata, baseline FEV₁ and <Visit data>.

The following SAS codes will be used:

```
proc mi data=<data2> out=<dataout> nimpute=1 seed=20905;
  by _imputation_;
  class <treatment> <region> <BackgroundMedStrata>
  <SmokingStrata>;
  var <treatment> <region> <BackgroundMedStrata>
  <SmokingStrata> <baseline> <visits>;
  monotone regression;
run;
```

3. Each multiple imputed dataset in Step 2 will be analyzed separately, as described in section 16.2.3 of the SAP.
4. The estimates (LS means, SE, CI and p-value) from the model analysis in Step 3 will be combined using Rubin’s combination rules for statistical inference.

Note: For secondary endpoints that are evaluated weekly, the following updates will be implemented for the first 2 steps:

1. MI model will contain weekly means at all weeks available to impute the data to create a monotone missingness pattern, so will be imputed missing values at any week (i.e Week 1, Week 2, etc.).
2. After this, the fully imputed dataset will include weekly means at weeks corresponding to scheduled visits in the MI model, and also only impute missing values at weeks corresponding to scheduled visits.

16.2.2.2. MI method – binary data

For the analyses of proportion of SGRQ, weekly mean total E-RS and Morning trough FEV₁ responders, an analysis will be performed using MI based on the missing data assumption MAR. This process will impute the continuous underlying data, as per 16.2.2.1 (morning trough FEV₁, SGRQ total score and weekly mean total E-RS), and then recalculate the binary outcome of responder or non-responder. The analysis will follow the steps below (Ratitch and O’Kelly, 2014, pp.124 - 127) (below the example uses morning trough FEV₁, but it is repeated also for other endpoints mentioned above):

- 1) Follow steps 1 and 2 from 16.2.2.1 for the continuous morning trough FEV₁ results.
- 2) For the imputed results re-calculate response, where a response is an improvement from baseline in morning trough FEV₁ of 100 mL.
- 3) Analyse each multiply imputed dataset separately, as described in section 16.2.3 of the SAP, producing LS Means, odd ratios and corresponding 95% confidence interval and p-value.
- 4) For the odds ratios:
 - a) Before applying Rubin’s rule, apply a normalising transformation to the odds ratios as well as their standard errors. The distribution of the log of odds ratios approximates to a normal distribution. Therefore, calculate the transformed values, where OR is odds ratio, Lower/Upper CL are the confidence interval estimates of the ORs:

$$OR_{norm} = \log(OR)$$

$$SE_{norm} = \frac{(\log(Upper\ CL) - \log(Lower\ CL))}{(2 \times 1.96)}$$

- b) Apply Rubin’s rule with PROC MIANALYZE to the transformed odds ratios with corresponding transformed standard errors.
- c) Back-transform the combined results as follows:

$$OR_{bt} = \exp^{OR_{norm}}$$

$$Lower\ CL_{bt} = OR_{bt} \times e^{(-1.96 \times SE_{norm})}$$

$$Upper\ CL_{bt} = OR_{bt} \times e^{(1.96 \times SE_{norm})}$$

- 5) For the odds of response per treatment arm
 - a) Take the LS means to be estimates of the log-odds of response per treatment arm and assume that they asymptotically tend to a normal distributions.

- b) Apply Rubin's rule with PROC MIANALYZE to the LS means.
- c) Transform the combined results by exponentiating to get the odds of response per treatment arm.

